8.11 Appropriateness of Measurements

All procedures used to measure the safety, tolerability, and PK profile of SAN-300 in this study were considered by the Sponsor and Investigators to be appropriate and necessary to obtain the required safety, tolerability, and PK data for the investigational product. The safety assessments used in this study, such as vital signs, ECG, and clinical chemistry and hematology monitoring, are widely used and are considered appropriate for monitoring patient health and well-being in this type of study.

The efficacy measures were selected to be generally comparable to published clinical studies in RA. The Investigators consider the measures to be standard assessments and endpoints for this disease. CRP and ESR measurements reflect the general inflammatory state of a patient and are components of the ACR Core Set Measurements.

The PD markers were chosen to allow assessment of the immunological effects of SAN-300. These assessments are designed to provide information relevant to their usefulness as biomarkers and measures of potential safety and efficacy. Changes in VLA-1 on lymphocytes and monocytes as well as changes in the levels of the pro-inflammatory cytokines IFN γ , TNF α , and IL-6 will be useful as potential biomarkers and indications of potential efficacy. VLA-1+ leukocytes, TNF α , and IL-6 are thought to be important drivers of inflammation in RA; IFN γ is a cytokine secreted by VLA-1+ T cells. Changes (specifically, any potential increases) in the levels of IFN γ , TNF α , and IL-6 will also be important safety markers.

Amendment 5: 28 Mar 2016

9 SAFETY REPORTING

Santarus maintains a robust pharmacovigilance system comprised of a governance framework and standard operating procedures supporting a systematic process for review, evaluation, and management of accumulating safety data from clinical trials and other sources to:

- Identify a potential new safety signal;
- Ensure that an investigational product's risks are adequately assessed and communicated to investigators, IRBs/ECs, and regulatory bodies during clinical development.

For this study, safety monitoring activities will include but are not limited to:

- Review and evaluation of single SAE occurrences in real-time as reported through the SAE reporting process as outlined in this section of the protocol;
- Review and evaluation, in real-time, of one or more occurrences of an uncommon SAE that is not commonly associated with product exposure;
- Findings and/or safety data obtained during this study will provide information for the overall review
 of safety that is conducted by Santarus on a routine basis. Santarus will report expeditiously any
 findings from clinical trials (ongoing or completed), epidemiological studies, pooled analysis of
 multiple studies, and findings from animal or in vitro testing that suggest a significant risk inhumans
 exposed to the study product.

Safety data collection for this study begins at the time of the subject's signing of the informed consent according to the operating definitions defined in this section of the protocol.

The Investigator is responsible for reporting all AEs that occur during the study, regardless of their relationship to study drug or their clinical significance.

9.1 Operating Definitions for Assessing Safety

9.1.1 Adverse Event

An AE is any untoward medical occurrence in a patient or clinical investigation patient administered a study product and which does not necessarily have a causal relationship with the treatment.

An AE can therefore be any unfavorable and unintended sign (that could include a clinically significant abnormal laboratory finding), symptom, or disease temporally associated with the use of a study product, without any judgment about causality (i.e., whether or not considered related to the study product).

Additionally, an event that is associated with study participation (regardless of administration of or relationship to study drug) should be treated as a reportable adverse event for this protocol (e.g., complications resulting from the taking of a blood sample or performance of a protocol required procedure).

Amendment 5: 28 Mar 2016

An AE does include the following:

- Exacerbation or worsening of a pre-existing illness.
 - NOTE: if the pre-existing illness is the disease under study, then "exacerbation" refers to an unexpected worsening from the condition at baseline.
- Increase in frequency or intensity of a pre-existing episodic event or condition.
- Condition detected or diagnosed after study product administration even though it may have been present prior to the start of the study.
- Symptom associated with disease not previously reported by the patient

An AE does not include the following:

- Medical or surgical procedures (e.g., surgery, endoscopy, tooth extraction, transfusion) as event terms; the condition that led to the procedure is the AE if it meets the definition of an AE.
- Situations where an untoward medical occurrence has not occurred (e.g., hospitalization for cosmetic elective surgery; and social and/or convenience admissions).
- Overdose of either study product or concurrent medication without any signs or symptoms.
- Symptoms associated with disease, which are consistent with the patient's usual clinical course; unless the subject experiences worsening of their symptom(s) or the symptom(s) meet the criteria for an SAE. Any medical condition present at the time of screening but does not worsen during the course of the study should be recorded as medical history.

9.1.2 Serious Adverse Event

A serious adverse event (SAE) is any AE that fulfills any of the following criteria:

- Results in death
- Is life-threatening
 - NOTE: the term "life-threatening" refers to an event in which the patient was at risk of death at the time of the event; it does not refer to an event which could hypothetically have caused death had it been more severe.
- Requires inpatient hospitalization or prolongation of existing hospitalization
 - NOTE: Complications that occur during hospitalization are AEs. If a complication prolongs hospitalization or fulfills any other serious criteria, the event is serious. "In-patient" hospitalization means the subject has been formally admitted to a hospital for medical reasons. This may or may not be overnight. It does not include presentation at a casualty or emergency room.
- Results in persistent or significant disability/incapacity

NOTE: The term disability means a substantial disruption of a person's ability to conduct normal life functions. This definition is not intended to include experiences of relatively minor medical significance such as uncomplicated headache, nausea, vomiting, diarrhea, influenza, or accidental

Amendment 5: 28 Mar 2016

trauma (e.g., sprained ankle) that may interfere or prevent everyday life functions but do not constitute a substantial disruption.

- Is a congenital anomaly/birth defect
- Is medically significant or requires intervention to prevent one of the outcomes listed above. NOTE: For example, allergic bronchospasm requiring intensive treatment in an emergency room or at home [see Section 8.10 on Assessing Hypersensitivity], blood dyscrasias, or convulsions that do not result in inpatient hospitalization, or the development of drug dependency or drug abuse.

9.2 Clinical Laboratory Abnormalities and Other Abnormal Assessments as AEs and SAEs

Abnormal laboratory findings (e.g., clinical chemistry, hematology) or other abnormal assessments (e.g., abnormal findings during examinations or ECG monitoring) that are judged by the investigator as **clinically significant** must be recorded as AEs or SAEs if they meet the definition of an AE or SAE. The investigator should exercise his or her medical and scientific judgment in deciding whether an abnormal laboratory finding or other abnormal assessment (including ECG monitoring) is clinically significant.

9.3 Method, Frequency, and Time Period for Detecting AEs and SAEs

At each visit, after the patient has had an opportunity to spontaneously mention any problems, the investigator should inquire about AEs by asking the following standard questions:

- 1. "Have you had any (other) medical problems since your last visit/assessment?"
- 2. "Have you taken any new medicines, other than those given to you in this study, since your last visit/assessment?"

9.3.1 Time Period for Detecting and Reporting of AEs and SAEs

From the time of informed consent through study completion/withdrawal, including the follow-up period.

9.3.2 Post-Study SAEs

Investigators are not obligated to actively seek SAE information in former study participants, but investigators are encouraged to notify the sponsor of any SAEs, of which they become aware occurring at any time after a patient has completed, discontinued or terminated study participation that they judge may reasonably be related to study treatment or study participation.

9.4 Documenting AEs and SAEs

All AEs that occur after the patient has signed the ICF and during the course of the study, regardless of causality or seriousness, will be assessed and recorded in the patient's medical records and in the CRF. In addition, SAEs must be documented on the paper SAE Report Form.

A separate paper SAE Report Form should be used for each SAE. However, if at the time of initial reporting, multiple SAEs are present that are temporally and/or clinically related, they may be reported on the same SAE Report Form.

SAN-300 Amendment 5: 28 Mar 2016

The investigator should attempt to establish a diagnosis for the event based on signs, symptoms, and/or other clinical information. In such cases, the diagnosis should be documented as the AE and SAE and not the individual signs/symptoms.

For clinically significant abnormal laboratory findings or other abnormal assessments meeting the definition of an AE or SAE, a diagnosis, if known (or clinical signs and symptoms if diagnosis is unknown), should be recorded by the investigator. If a diagnosis is unknown and clinical signs and symptoms are not present, then the abnormal finding should be recorded. When documenting as an SAE on the SAE Report Form, relevant laboratory data should either be recorded in the 'Details of Relevant Assessments' section of the SAE Report Form (including the reference range and units) or copies of the laboratory report (with reference ranges and units) should be sent with the SAE Report Form.

The SAE Report Form should be completed as thoroughly as possible and signed by the investigator or his/her designee before transmittal to Product Safety. It is **very important** that the investigator provide his/her assessment of causality to study product at the time of initial SAE reporting.

9.5 Follow-up of AEs and SAEs

All AEs, regardless of seriousness, must be followed until resolution, until the condition stabilizes, until the event is otherwise explained, or the subject is lost to follow-up. The investigator is responsible to ensure that follow-up includes any supplemental investigations as may be indicated to elucidate as completely as practical the nature and/or causality of the AE. This may include additional laboratory tests or investigations, histopathological examinations, relevant hospital records (i.e. discharge summary), or consultation with other health care professionals.

Product Safety may request that the investigator perform or arrange for the conduct of supplemental measurements and/or evaluations. If a patient dies during participation in the study or during a recognized follow-up period, Product Safety should be provided with a copy of any postmortem findings, including histopathology.

For SAEs, new or updated information should be recorded on the originally completed paper SAE Report Form and all changes signed and dated by the Investigator or designee. By signing the SAE Report Form, the investigator or designee attests to the accuracy and completeness of the data and that he/she has reviewed and approved the report being submitted. The investigational sites IRB/IEC must be notified about SAEs in accordance with the requirements of the governing IRB/IEC.

9.6 Assessment of Causality

The Investigator's assessment of the relationship to study drug of an AE is part of the documentation process but is not a factor in determining whether or not it is reported. All AEs, regardless of causality, must be reported. The blind should not be broken for the purpose of making this assessment. If there is uncertainty as to whether a clinical observation is an AE, the event should be reported.

The relationship of the event to the study drug should be determined by the Investigator according to the following criteria:

Not related An event for which sufficient data exist to indicate that the etiology is unrelated to the drug.

Amendment 5: 28 Mar 2016

Unlikely related An event that does not follow a reasonable temporal sequence relative to administration

of the drug. However, causality from the drug cannot be ruled out.

Possibly related An event that follows a reasonable temporal sequence relative to administration of the

drug; that follows a known or expected pattern of response to the drug; but that could

readily have been produced by other factors.

Probably related An event that follows a reasonable temporal sequence relative to administration of the

drug; that follows a known or expected pattern of response to the suspected drug; and that could not be reasonably explained by the known characteristics of that patient's

clinical state.

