1.3 Clinical Experience with SAN-300

A total of 66 healthy volunteer subjects and two patients with active RA participated in Phase 1 Study C2011-0301 (301), in which 45 healthy subjects and one patient with active RA received single doses of SAN-300 via IV infusion or SC injection. Detectable serum SAN-300 concentrations were not observed in the majority of subjects receiving SAN-300 0.03 mg/kg to 0.3 mg/kg IV. In subjects receiving SAN-300 0.6 to 2.0 mg/kg, there was a trend towards increasing serum SAN-300 concentrations with increasing dose. Receptor occupancy was essentially complete (\geq 90%) over a wide range of doses tested for both the IV and SC formulations (by 72 hours postdose for > 0.8 mg/kg IV and by 24 hours postdose for 2.0 to 6.0 mg/kg SC). Receptor occupancy was also durable, with median occupancy remaining at approximately \geq 70% at Day 8 for all dose groups administered SAN-300 SC.

Amendment 5: 28 Mar 2016

SAN-300 was generally well tolerated in this study. Mild to moderate infusion reactions occurred upon IV administration of SAN-300 doses from 0.8 to 2.0 mg/kg; all events improved with or without treatment by 72 hours and none led to withdrawal from the study. Among subjects receiving SC SAN-300 at doses ranging from 2.0 to 6.0 mg/kg, headaches and mild injection-site reactions were most common. No severe or serious infections were reported in any group. No clinically meaningful changes from baseline were observed after SAN-300 dosing for biochemistry parameters and for the majority of hematologic parameters tested. Transient, Grade I/II reductions from baseline in absolute neutrophil count (ANC) were observed in 12 subjects who received SAN-300. None of these cases were associated with concurrent infections, and all resolved. Two subjects tested positive for treatment-emergent anti-SAN-300 antibodies; no immunogenicity-related adverse events were observed in these subjects. The safety findings from this Phase 1 study support further development with the proposed multiple ascending dosing regimen in patients with RA.

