8.2.3 Treatment-Emergent Adverse Events Related to Study Drug

Related AEs are the AEs with "Related" or "Possibly Related" for causality. TEAEs with missing relationship to study drug will be considered "related" in the tabular summaries but data listings will show relationship as missing.

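### Protocol 9.6 has no causality grade for a well-timed event without a known or expected pattern, and the SAP definitions of related do not match the protocol's four grades.

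*Protocol*

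**What the plan says.** Protocol 9.6 tells the investigator to rate each event's relationship to study drug by four definitions.

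- *Not related*: "An event for which sufficient data exist to indicate that the etiology is unrelated to the drug".
- *Unlikely related*: "An event that does not follow a reasonable temporal sequence relative to administration" of the drug, with the rider that a causal role still cannot be excluded.
- *Possibly related*: reasonable timing, and "drug; that follows a known or expected pattern of response to the drug; but that could" readily have another origin.
- *Probably related*: reasonable timing, and "drug; that follows a known or expected pattern of response to the suspected drug; and that could not be reasonably explained by" the patient's clinical state.

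The same section separates grading from reporting: "All AEs, regardless of causality, must be reported".

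Protocol 11.5 tabulates AEs by relationship, and the SAP plans Table 14.3.1.7 for drug-related TEAEs. SAP 8.2.3 states: "Related AEs are the AEs with 'Related' or 'Possibly Related' for causality". SAP 8.2.1 instead counts events with a possible or definite relationship. Both SAP sections count a missing relationship as related.

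On prior experience, Protocol 1.3 describes a Phase 1 study "in which 45 healthy subjects and one patient with active RA received single doses of SAN-300 via IV infusion or SC injection". Protocol 3.2.3 presents the current trial as the first multiple-dose experience.

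**The concern.** The primary objective is safety and tolerability. A first repeat-dose study may show reactions that single dosing did not. Repeat dosing in monkeys produced anti-drug antibodies (Protocol 1.2.2), and immunogenicity is a secondary objective here. For such reactions a known pattern may not yet exist, yet the scale makes a known or expected pattern a condition of both grades that express a drug relationship.

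What is at stake is attribution. Two investigators who see the same unfamiliar, well-timed event have no common rule for grading it. Whether it reaches the related-AE tabulation then depends on which definition each of them bends.

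**Working it through.** No statistical figure is involved, so the check is to enumerate the definitions.

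**Inputs (Protocol 9.6).** There are three yes/no attributes: reasonable timing (T), known or expected pattern (P), and another reasonable explanation (O). Two assumptions are made. The event lacks sufficient data to be called *Not related*, and the alternative-explanation clauses of *Possibly* and *Probably related* are treated as complements. This gives 2 × 2 × 2 = 8 combinations.

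**Grades as written**

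| T | P | O | Grade that fits | Combinations |
|---|---|---|---|---|
| no | any | any | Unlikely related | 4 |
| yes | yes | yes | Possibly related | 1 |
| yes | yes | no | Probably related | 1 |
| yes | no | any | none | 2 |

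Total: 4 + 1 + 1 + 2 = 8, of which 2 have no grade. These are combinations of attributes, not a forecast of the share of events.

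**If the pattern condition is removed.** T = no gives *Unlikely related* (4), T = yes with O = yes gives *Possibly related* (2), and T = yes with O = no gives *Probably related* (2). Then 4 + 2 + 2 = 8, and no combination is left without a grade.

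**How much pattern is known.** Protocol 1.3 gives 45 healthy subjects and one patient with RA who received the drug: 45 + 1 = 46 people, single doses only.

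**Labels set side by side**

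| Source | Labels |
|---|---|
| Protocol 9.6 | Not, Unlikely, Possibly, Probably related |
| SAP 8.2.1, counted as related | possible, definite |
| SAP 8.2.3, counted as related | Related, Possibly Related |

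*Definite* and a plain *Related* do not exist on the protocol scale. *Probably related*, the strongest protocol grade, is named in neither SAP definition.

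**The case against.** The strongest reply is that little in the plan depends on this scale. Most of it stands.

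- All AEs are reported whatever their grade, and SAEs go to Product Safety within 24 hours (Protocol 9.7). The SAP safety endpoint is TEAE incidence. Tables 14.3.1.2 to 14.3.1.6 and Listing 16.2.7.1 do not use relatedness.
- A reader might infer that the gap distorts each dose-escalation decision. The documents do not support this: the Safety Committee reviews AEs, laboratory results, vital signs and withdrawals (Protocol 3.1 and 5.1), with no filter by causality.
- A reader might infer that it weakens the stopping rules. The third criterion in Protocol 3.4.1 rests on the opinion of the investigator or Sponsor about study participation, and it does not cite 9.6. A clinically significant Appendix 1 infection triggers the rules in 3.4.1 and 3.4.2 with no causality test.
- A reader might take the known pattern to mean the Phase 1 findings alone. The text also admits expected patterns, and the protocol anticipates more: parasite recrudescence in monkeys (1.2.3), hypersensitivity (8.10), cytokine increases (8.11) and opportunistic infections (Appendix 1). But 9.6 does not define expected, so sites may draw the line differently.
- A reader might infer a one-way bias towards a cleaner profile. *Unlikely related*, with its rider that causality is not excluded, is a tempting default. But its timing condition also fails here. An investigator could equally stretch expected and choose *Possibly related*, or leave the field blank, which the SAP counts as related.

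None of these points supplies the missing grade. The missing-value rule covers blanks only, and Protocol 9.4 stresses giving causality when an SAE is first reported.

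**Conclusion.** The gap is real on the literal wording. An event with reasonable timing, no known or expected pattern and no proven other cause meets none of the four definitions, and neither related grade is open to it. The consequence is inconsistent grading and possible loss of such events from the Protocol 11.5 by-relationship tabulation and Table 14.3.1.7.

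The number affected cannot be computed. It runs from none, if every well-timed event is of a known or expected kind or has a proven other cause, to every well-timed event that is neither. The direction is not established either. The conclusion assumes that the conditions in 9.6 are cumulative, which is how they are written.

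Severity: should-fix. The mismatch between the SAP labels and the protocol scale affects the same table and belongs in the same correction.

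**What to change.** 1. In Protocol 9.6, make the known pattern supporting evidence and not a required condition. *Possibly related*: reasonable timing, but other factors could also have produced the event. *Probably related*: reasonable timing, and not reasonably explained by the patient's clinical state. Use the same text in the CRF guide.
2. Rewrite SAP 8.2.1 and 8.2.3 with the protocol's four grades, so that *Possibly* and *Probably related* both count as related. Keep the missing-as-related rule.
3. SAP 3.5 reports 41 subjects already randomized, so rewording alone comes late. If the blind is still intact (Protocol 5.3 holds it until database lock), have investigators re-grade all AEs under the revised text. Re-grading only those rated *Unlikely* or *Not related* could move ratings in one direction only.
4. If the blind has been broken, list the well-timed events rated *Unlikely* or *Not related* and state the limitation in the report.

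The cost is a short wording change in each document, a small re-grading effort, and possibly more events counted as related.

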9.7 Prompt Reporting of SAEs to Product Safety

SAEs must be reported promptly to Product Safety once the investigator determines that the event meets the protocol definition of a SAE.

Prompt reporting of a SAE requires:

- Completion and transmission of the SAE Report Form to Product Safety via fax within 24 hours of the investigator's knowledge of the event. In parallel, a corresponding AE with the SAE details should be entered into the AE CRF within 48 hours of submitting the paper SAE Report Form.
- Prompt reporting of additional information for previously reported SAEs should follow the same reporting timeframe as initial reports. In addition, the corresponding AE in the AE CRF (as applicable) should be updated to ensure all data points documented in the AE CRF are aligned with the matching data points on the paper SAE Report Form.

